#### Speech and Text Measures.

1. The monologue speech task (Agurto et al., *in press*; Higgins and Stitzer, 1989; Wardle et al., 2011) measures spontaneous speech, initially developed to determine how the amount of speech may be changed by acute effects of alcohol and amphetamine (Higgins and Stitzer, 1989). The task consists of a 5-min period during peak drug effects in which subjects are allowed to talk while they are alone in a room with a voice recorder. Subjects are told they are allowed to talk as much or as little as they like on any topic. All recorded speech is transcribed by a professional blind to drug condition for analysis. The primary outcome measure is the percent accuracy in classification of drug condition based on frequent word occurrences during the 5-min task.

#### *Analytic approach*

- a. Acoustic features: Acoustic features will be extracted from five categories, including voice stability (jitter, shimmer, and voice breaks), pitch variations, spectral characterization, vowel space, and temporal features. Feature extraction involves the software Praat and Python.
- b. Semantic features: Total number of words and frequency of word occurrences will be used to compare across the drug conditions. Text derived from speech will be preprocessed with the Natural Language Toolkit (NLTK). Words will be counted from a tokenized word list, which is created by use of Treebank tagger, to identify parts of speech, and WordNet, to lemmatize words into tokens.

- c. Classification: We will use a machine learning approach to determine the number of word occurrences in text in each drug condition. This approach incorporates Random Forests, which generates decision trees based on individual word predictors.
- 2. For written self-report, participants will receive the following instructions: "For the next 10 minutes, you are asked to attend to how you are feeling right now. During this time, write down as little or as much as you like about any thoughts or sensations you are having." All writing will be converted into text for analysis. The primary outcome measure is the degree of distinction between drug conditions based on frequent word occurrences, in parallel to the 5-min speech task.

*Analytic approach*

- a. Semantic features: Total number of words and frequency of word occurrences will be used to compare across the drug conditions. Text derived from speech will be preprocessed with the Natural Language Toolkit (NLTK). Words will be counted from a tokenized word list, which is created by use of Treebank tagger to identify parts of speech, and WordNet, to lemmatize words into tokens.
- b. Classification: We will use a machine learning approach to classify the number of word occurrences in the written text. This approach incorporates Random Forests, which generates decision trees based on individual word predictors.

*Self-Report Measures.*

- 1. The Addiction Research Center Inventory (ARCI; Martin et al., 1971) is a 53-item true/false questionnaire, including a 12-item Marijuana (M) subscale specific to cannabis. We will focus our analyses on the M scale.
- 2. The Profile of Mood States (POMS; McNair et al., 1971) is a 72-item questionnaire used to assess momentary mood states across 8 subscales: Anxiety, Depression, Anger, Vigor, Fatigue, Confusion, Friendliness, and Elation. Participants will indicate how they feel at that moment in relation to 72 adjectives on a 5-point scale from "Not at all" (0) to "Extremely" (4).
- 3. The Drug Effects Questionnaire (DEQ; Morean et al., 2013) is comprised of 100 mm visual analog scales (VAS) to provide ratings to five questions: "Do you feel any drug effect?" ("None at all" to "A lot"); "Do you like the effects that you are feeling now?" ("None at all" to "A lot"); "Do you dislike the effects that you are feeling now?" ("None at all" to "A lot"); "Are you high?" ("Not at all" to "Very"); and "Would you like more of what you consumed, right now?" ("Not at all" to "Very much"). The measure of primary interest is the "feel" question.
- 4. The 5 Dimensions of Altered States of Consciousness (5D-ASC; Studerus et al., 2010) scale consists of 94 statements describing common features of altered states of consciousness (ASC), independent of their means of induction. In developing the scale, 11 ASC induction mechanisms including THC were used. The 5D-ASC contains five dimensions of ASC: Oceanic Boundlessness, Dread of Ego Dissolution, Visionary Restructuralization, Acoustic Alterations, and Vigilance Reduction (Studerus et al., 2010). Subjects respond to statements on a 100 mm visual analog scale indicating how they feel relative to their normal waking consciousness and the degree to which they experienced each item during that day's session. The 5D-ASC is often used in studies of 'classical psychedelics' which bind 5HT-2A serotonin receptors. Although THC was included in the development of this scale, we note that measures of THC effects will

be exploratory. We know of no previous THC studies that have incorporated the 5D-ASC. The 5D-ASC will be administered once at the end of each session.

5. The State Mindfulness Scale (SMS; Tanay and Bernstein, 2013) is comprised of two subscales, including a 15-item mindfulness-of-mind subscale and six-item mindfulness-of-body subscale (sample item: "I clearly physically felt what was going on in my body"). With each item, participants provide ratings on a five-point scale from "Not at all" to "Very much." The SMS will be administered once at the end of each session.

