## Protocol

Title: Age-Related Effects of THC (“Effects of drugs on behavior – ART” on the consent form)

Principal Investigator: [name], Ph.D.

Co-Investigators: [name]. and [name].

**Objectives:** **1)** To determine whether adolescents (defined here as ages 18-20) are at greater risk to acute oral 7.5 and 15 mg  $\Delta 9$ -tetrahydrocannabinol (THC) intoxication than adults (defined here as ages 30 to 40), **2)** to develop a sensitive behavioral measure to detect intoxication levels of THC, and **3)** to determine whether age-related drug effects are detectable using electroencephalography (EEG).

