There is limited knowledge on the effects of THC in adolescents vs adults. One recent report compared responses to vaporized cannabis in heavy adolescent vs adult cannabis users (Mokrysz et al., 2016) and found that the adolescents were less sensitive to the drug on most measures. However, their findings were complicated by several factors: i) the study used vaporized cannabis, which may have other constituents and does not offer full control of the dose, ii) the participants were heavy users, making it difficult to determine the influence of prior drug exposure, and iii) the participants were not drug-free at the time of testing. Prior exposure to THC can lead to tolerance, and adolescents and adults may differ in the rate at which they develop tolerance, consistent with changes in CB1R receptor function (Burston et al., 2010; Cha et al., 2006; Murray, Pabon, de Wit, unpublished finding; Quinn et al., 2008; Wiley et al., 2007). Our study will compare adolescent (here, aged 18 to 20) and adult (here, aged 30 to 40) responses to THC in relatively light cannabis users who are drug-free at the time of testing.

A second goal of this study is to develop a sensitive measure of THC intoxication by analyzing text from samples of subjects' spontaneous speech. We have used analyses of speech production and semantic content to assess changes in mental state during acute intoxication with several other drugs, including MDMA and methamphetamine (Agurto et al., *in press*; Baggott et al., 2015; Bedi et al., 2014; Wardle et al., 2011), but never with THC. The application of speech and text analyses to THC effects is a promising avenue to develop more sensitive behavioral measures of THC intoxication. Importantly, the accurate detection of cannabis intoxication is a major public health concern. Drugs can change a range of features of human speech, including the quantity, speed, fluency, volume, and acoustic features. In addition, drugs can affect many aspects of semantic content including perceived features of drug effects. By applying sensitive quantitative techniques to analysis of speech and text samples, it may be possible to extract features that reflect intoxication with this drug.

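### The word-based outcomes meant to give a behavioral measure of THC intoxication do not separate stating one's drug state from a change in language, mainly in the written task

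*Combined protocol and SAP*

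**What the plan says.** The Objectives give the second aim as "to develop a sensitive behavioral measure to detect intoxication levels of THC". Significance & Innovation restates it as an effort to "develop a sensitive measure of THC intoxication by analyzing text from samples of subjects' spontaneous speech" and adds the motive that "the accurate detection of cannabis intoxication is a major public health concern". The same section says that "drugs can affect many aspects of semantic content including perceived features of drug effects", so content about felt effects is within the intended scope.

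Speech and Text Measures then describes two tasks.

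- **Monologue (item 1).** Five minutes of speech on any topic. "The primary outcome measure is the percent accuracy in classification of drug condition based on frequent word occurrences during the 5-min task". Acoustic features are also extracted.
- **Written self-report (item 2).** Ten minutes of writing. Participants are told "you are asked to attend to how you are feeling right now" and to "write down as little or as much as you like about any thoughts or sensations you are having". "The primary outcome measure is the degree of distinction between drug conditions based on frequent word occurrences", in parallel with the speech task.

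For both tasks the text is tagged, lemmatized and counted, and Random Forests are built on individual words. The protocol describes no masking or removal of drug-related words and no run without them. It sets no accuracy threshold and no comparison with the DEQ or the Addiction Research Center Inventory (ARCI).

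**The concern.** A participant who writes *I feel high* has answered the question that the prompt asks. The classifier can use that word to identify the session, and the primary outcome rises. Nothing in the word-based analysis shows whether THC changed how the person uses language or whether the person reported a state when asked for it. The second possibility is close to a free-text DEQ.

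The protocol itself treats self-report and behavioral measures as different kinds, under separate headings. A good classification result from the written task could nevertheless be presented as the behavioral measure of Objective 2. If the separation came only from people naming their state, the trial would have shown that they can report intoxication, which the DEQ already measures. What is at stake is how Objective 2 may be described. The DEQ *feel* outcome, on which the sample size rests, is not affected.

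**Working it through.** The protocol gives no accuracy, threshold or sample size for the text outcomes, so there is no figure to reproduce. The check is a reading, followed by an illustration.

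**Reading**

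1. *Aim:* a behavioral measure (Objectives).
2. *Input:* a task named self-report whose prompt asks for feelings, thoughts and sensations (Speech and Text Measures, item 2).
3. *Predictors:* single lemmatized words, with no exclusion list (both items).
4. *Vocabulary:* the DEQ items use the words *drug* and *high* (Self-Report Measures). The DEQ is first given at +60 min (Drug Administration Sessions) and the written task follows at +80 min (Timeline), a gap of 80 − 60 = 20 minutes.
5. *Planned separation:* none for the word-based outcomes. For speech, the acoustic features (voice stability, pitch, spectral, vowel-space and temporal measures) do not depend on which words are chosen. Total word count, planned for both tasks, is also not driven by particular disclosure words.

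**Illustration**

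From Participants and Research Design, 20 participants × 3 sessions give at most 60 texts per task, 20 per condition. Assume that one disclosure word appears in a proportion p0, p7.5 and p15 of placebo, 7.5 mg and 15 mg texts, rising with dose, and that no other word is informative. The best rule is: word absent, call placebo; word present, call 15 mg. Then

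- three-way accuracy = [(1 − p0) + 0 + p15] / 3, against 1/3 by chance;
- 15 mg versus placebo accuracy = [(1 − p0) + p15] / 2, against 1/2 by chance.

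| Assumed p0 / p7.5 / p15 | Three-way | 15 mg vs placebo |
|---|---|---|
| 2% / 15% / 30% | (0.98 + 0.30)/3 = 42.7% | 1.28/2 = 64% |
| 5% / 20% / 40% | (0.95 + 0.40)/3 = 45.0% | 1.35/2 = 67.5% |
| 10% / 40% / 70% | (0.90 + 0.70)/3 = 53.3% | 1.60/2 = 80% |
| 5% / 40% / 75% | (0.95 + 0.75)/3 = 56.7% | 1.70/2 = 85% |
| 10% / 60% / 90% | (0.90 + 0.90)/3 = 60.0% | 1.80/2 = 90% |

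As a yardstick, which the plan does not supply, treat the 60 texts as independent. This is a simplification, since each person gives three. For a Binomial(60, 1/3) count, P(X ≥ 27) = 0.040 and P(X ≥ 26) = 0.068, so 27/60 = 45% is the smallest result above chance at one-sided 5%. For 15 mg versus placebo, 26/40 = 65% is the smallest (P = 0.040).

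The lowest row has an expected 60 × 0.427 = 25.6 correct. The number correct there is Binomial(20, 0.98) plus Binomial(20, 0.30), which reaches 27 about 33% of the time. The second row sits exactly at the bar, and the other three exceed it.

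**The case against.** The strongest reply is that felt effects are meant to count. Significance & Innovation names them as part of semantic content, and Hypothesis 2 asks only for sensitive indices of intoxication, not for indices free of disclosure. This stands: a result driven by disclosure would still support Hypothesis 2 as written. The difficulty is confined to the word *behavioral* in Objective 2.

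Other points also stand, in whole or in part.

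- The protocol already calls the written task a self-report, and its restated goal refers to spontaneous speech. In the monologue, disclosure enters only if the speaker chooses to comment on the drug state. The point therefore bears mainly on the written task.
- A reader might infer that the trial could never tell disclosure from language change. The documents do not support that. Acoustic features and total word counts are planned, word frequencies are compared across conditions, and the texts can be re-run later. What is missing is a pre-specified analysis of the primary word-based outcomes.
- A reader might also infer that self-disclosure would count as success. The plan defines no success criterion, and its outcomes use frequent words, so rare ones may drop out.
- *Placebo* is a weak example of a disclosure word, because participants learn which drug they received only after the final session and the consent text is not available.
- The plan describes no detection setting in which users conceal their state, and the Background also wants the measure for comparing sources of risk. Disclosure does not defeat that second purpose.
- A list of single words cannot mask phrases. State words such as *dizzy*, *sleepy* or *relaxed* would remain, so masked accuracy does not isolate behavioral signal either.

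**Conclusion.** The point holds as a limit on interpretation. Words that disclose the drug state can raise the primary word-based outcomes, and no planned analysis of those outcomes separates this from a change in language. The written task is the main case; the monologue is less exposed, and its acoustic features and the total word counts are not affected in the same way. The unmasked results remain valid as indices of intoxication under Hypothesis 2. It would go too far to conclude that they are invalid or that Objective 2 as a whole fails.

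The size is unknown. The figures of 43% to 60% rest on invented word rates, on a single informative word, and on a best rule known in advance, whereas a Random Forest would have to learn it from at most 60 texts with many words. They show that moderate disclosure could be enough to exceed chance, and that low disclosure might not be.

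**What to change.** Before unblinding, meaning before any text is linked to its drug condition, add the following to the analytic approach.

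1. Fix a short list of single-word disclosure terms: drug, dose and capsule words, words from the DEQ items, and intoxication words such as *high*, *stoned*, *sober* and *buzzed*.
2. Run the same classifier on each task with and without these terms, and report both results.
3. Present the unmasked written-task result as a self-report measure.
4. Describe a text result as behavioral under Objective 2 only if the separation persists without the terms or is supported by the acoustic features. State that other state words remain in the masked text.

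The cost is one extra run of the same classifier on each task's texts, with no new data and no change to the sessions. The list will be somewhat arbitrary: some DEQ words, such as *like* and *more*, are common in ordinary language. The accuracy behind any behavioral claim will probably be lower. Fixing the list in advance matters because one chosen after seeing which words drove the classification would be open to challenge.

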#### Behavioral Measures.

1. The Simple Reaction Time task (SRT; Leth-Steensen et al., 2000) is used to measure inattention. Participants execute a key press as quickly as possible to a target presented on the computer screen at variable intervals. The difference between a participant's mean and modal reaction time (RT) represents the proportion of unusually long RT's, which are inferred to reflect momentary lapses in attention. Greater deviations of mode scores indicate more lapses in attention (De Wit, 2009; McCloskey et al., 2010). This task takes 2-3 minutes to complete.
2. The Stop Task (Logan et al., 1997) is designed to assess a participant's ability to inhibit a prepotent motor response. Subjects are instructed to respond as quickly as possible when a certain letter (Go signal) is presented visually on a computer screen, and to inhibit (stop) their responses when a tone is presented. The tone is presented on random trials and at different delays following each letter presentation. The delays to the Stop signal are varied systematically according to the participant's performance: the delay to the tone is adjusted until the subject inhibits (stops) his or her responses on approximately 50% of trials. Once the Stop signal delay has been adjusted to this 50% criterion, the time required for the subject to stop the go response is determined. The primary measure of interest is the Stop reaction time (Stop RT), which is calculated by subtracting the final mean delay at which the tone is presented from the mean Go reaction time (Go RT), or the latency to respond to the letter presentation, which is a secondary measure. Both reaction times are measured in milliseconds. This task takes 7 mins.
3. The N-Back Task (Gevins and Cutillo, 1993) assesses executive attention and working memory. Participants respond when the current visual and audio stimulus (a letter) is the same as the one presented  $n$  trials earlier; where  $n$  is either 1, 2, or 3. This task takes 10 mins.
4. The Time Production Task (Sewell et al., 2013) assesses the rate of participant's internal clock relative to actual time. Participants will be instructed to press and hold a key for 10, 20, 30, and 40 seconds in a randomized order while attending to distractor stimuli. The ratio of produced time to actual time is the outcome measure of interest. This task takes 3 mins.

Cardiovascular Measures. Blood pressure and heart rate will be monitored every 30 min using portable blood pressure cuffs, to track the cardiovascular effects of the drug, and ensure participant safety.

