**Participants.** Participants will include 20 healthy male and female volunteers, half of whom will be aged 18-20 and the other half aged 30 to 40. The N of 20 participants is based on a reported effect size ( $f = 0.403$ ; Mokrysz et al., 2016) on our primary outcome measure (group x drug interaction on Drug Effects Questionnaire: "Feel"), which requires a sample size of 16 for at least 80% power at an alpha of 5% (G\*Power). The groups will be matched on number of males and females and on body mass index. Subjects will be excluded if they have a history of psychosis, nursing or pregnant, planning to become pregnant, or have a body mass index outside of 19 to 26. Subjects must have at least a high school education and fluency in English. Other criteria include individuals who have used the drug between 1 to 20 times lifetime and 0 times in last 30 days. Qualifying participants will agree to abstain from alcohol for 24 hours and other recreational drugs for at least 2 days before each session. They will be informed that breath and urine samples will be obtained on each session to verify abstinence. Participants will also be asked to fast 4 hours before the behavioral laboratory session.

**Drug.** THC (Marinol® [dronabinol]; Solvay Pharmaceuticals) will be orally administered in doses of 7.5 mg and 15 mg, in opaque capsules with dextrose filler. Placebo capsules contain only dextrose. The 15 mg dose reflects the amount of THC in one-half of a cannabis cigarette containing 0.2 g of 15% THC. These doses of THC are known to produce performance impairments as well as subjective intoxication (Broyd et al., 2016; Hartman and Huestis, 2013; Pabon and de Wit, 2019).

**Orientation Session.** During an initial, 30-min orientation session, study procedures will be explained and participants will read and sign a consent form. Participants will then practice the tasks and questionnaires that will be administered during the subsequent study sessions. A urine sample will be obtained to confirm abstinence from cannabis; subjects will be instructed to maintain abstinence from cannabis throughout the study and refrain from any use of drugs or alcohol for 24 before and 6 hours after each drug administration session. Participants will also be told to have a normal night's sleep and to fast 4 hours before the session; a standardized snack will be provided.

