2. The Flanker Interference Task (Endrass et al., 2008; Eriksen and Eriksen, 1974) is an error monitoring task involving visual stimuli. A visual target stimulus is flanked by non-target stimuli that may either be congruent, incongruent, or neutral to the target response. Experimental stimuli will be displayed with Presentation software (Neurobehavioral Systems, San Francisco, CA) on an LCD monitor placed at a comfortable viewing angle. Trials begin with a fixation mark for 1100–1700 ms. 100 ms after onset of Flanker arrows, a central target arrow will appear for 30 ms. Subjects are to indicate the direction of the central target arrow with a button press. 500 trials will be presented, with 150 being compatible trials (with congruent flanker and target errors) and 350 being incompatible trials in pseudo-random order. To maintain time pressure and ensure an adequate number of error trials, subject response times will be recorded and subjects will be prompted to move more quickly based on a moving average of the past 50 correct trials. Error-related negativities (ERNs) will be recorded. This task takes 5 mins.

Timeline:

9:00	-30	Arrival, breath and urine tests
9:15	-15	Subjective and cardiovascular measures (baseline)
9:30	0	Capsule administration
10:00	+30	Standardized snack
10:30	+60	Subjective and cardiovascular measures
10:50	+80	Written self-report
11:00	+90	Subjective and cardiovascular measures, speech and behavioral tasks
11:30	+120	Subjective and cardiovascular measures
11:40	+130	Move to CNPRU and prepare EEG for recording
12:10	+160	EEG: auditory oddball P300 and Flanker task
12:30	+180	Subjective and cardiovascular measures
1:30	+240	Subjective and cardiovascular measures, 5D-ASC, SMS, End of Session Questionnaire

**Data Analyses:** The effects of the drug on subjective, behavioral, and cardiovascular measures will be assessed with mixed analysis of variance, with the between-subjects factor of group (adolescent, adult) and within-subjects factors of drug (placebo, 7.5 mg, 15 mg THC) and time (within session). Repeated measures ANOVA will compare ERPs including P300 amplitude between THC and placebo sessions.

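### Stop RT is scored from the mean Go RT although 50% tracking identifies the median, so changes in Go RT skew or in omissions could shift it with stopping ability unchanged

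*Combined protocol and SAP*

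**What the plan says.** Under Behavioral Measures, item 2, the Stop Task "is designed to assess a participant's ability to inhibit a prepotent motor response". During the task "the delay to the tone is adjusted until the subject inhibits (stops) his or her responses on approximately 50% of trials". The same item continues: "The primary measure of interest is the Stop reaction time (Stop RT"), and this is "calculated by subtracting the final mean delay at which the tone is presented from the mean Go reaction time (Go RT"). Mean Go RT is the task's secondary measure.

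The item gives no response deadline, no rule for go trials without a response, no trimming of long Go RTs and no median or percentile scoring. Under Data Analyses, "The effects of the drug on subjective, behavioral, and cardiovascular measures will be assessed with mixed analysis of variance", with factors for group, drug and time. No adjustment of Stop RT for the shape of the Go RT distribution is described.

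Item 1 of the same section, the Simple Reaction Time task, uses the difference between mean and modal RT as an index of "unusually long RT's, which are inferred to reflect momentary lapses in attention".

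**The concern.** A delay tracked to 50% inhibition locates the middle of the Go RT distribution, not its mean. The two agree when Go RTs are symmetric and separate when there is a long upper tail. The plan's own lapse index in item 1 relies on that kind of separation, because it reads the distance between the mean and the centre of the RT distribution as inattention. In item 2 a similar distance is added to a score meant to reflect inhibition.

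A person's stable skew cancels in the within-subject drug contrast. A change in skew, or in omissions, between placebo and THC sessions does not cancel. If that change also differs between age groups, it enters the group x drug interaction. A drug effect or an age difference on Stop RT could then be read as a difference in inhibition when stopping ability had not changed.

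**Working it through.** The plan gives no numerical Stop RT, so there is no figure to reproduce. The check has an algebraic part and a simulation.

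**Algebra.** In the independent race model, a response escapes on a stop trial when Go RT < delay + Stop RT. When half of the responses escape:

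- delay + Stop RT = median Go RT, so true Stop RT = median Go RT - delay.
- Plan's score = mean Go RT - delay = true Stop RT + (mean - median Go RT).

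**Simulation inputs (all assumed).** Go RT is ex-Gaussian with mu 400, sigma 40 and tail parameter tau. True Stop RT is 220 ms (trial SD 20) and never changes. There are 192 go and 64 stop trials and a one-up, one-down staircase with 50-ms steps. The delay is averaged after the first 16 stop trials.

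**Skew alone.**

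| tau (ms) | Mean Go RT | Median Go RT | Gap | Plan's score | Median - delay |
|---|---|---|---|---|---|
| 50 | 450 | 442.4 | 7.6 | 224 | 216 |
| 75 | 475 | 459.7 | 15.3 | 229 | 214 |
| 100 | 500 | 476.3 | 23.7 | 236 | 212 |
| 150 | 550 | 509.2 | 40.8 | 250 | 210 |

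The two scores differ by the gap, as the algebra requires (for example 250 - 210 = 40 at tau 150). The median-based score lies a little below 220 because a coarse staircase on a skewed distribution settles at a slightly long delay.

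**Controls.** With symmetric Go RTs (normal, mean 450, SD 80) the plan's score is 220.0 ms. Slowing every response by 50 ms gives 219.6 ms. Neither symmetric variation nor pure slowing biases it.

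**Lapses on 10% of trials.** Late lapses add an exponential delay with mean 400 ms; omissions give no response. The percentile score is the Go RT at the percentile equal to the observed response rate on stop trials, minus the mean delay. Entries are Stop RT in ms.

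| Scenario | tau | Plan's score | Percentile score, omissions dropped | Percentile score, omissions ranked slowest |
|---|---|---|---|---|
| No lapses | 50 | 224 | 217 | 217 |
| Late, all recorded | 50 | 254 | 214 | 214 |
| Late, 1000-ms deadline | 50 | 230 | 212 | 214 |
| Omissions | 50 | 212 | 205 | 213 |
| No lapses | 75 | 229 | 214 | 214 |
| Late, all recorded | 75 | 258 | 211 | 211 |
| Late, 1000-ms deadline | 75 | 232 | 209 | 211 |
| Omissions | 75 | 215 | 200 | 210 |

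Shifts from the no-lapse row:

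- Plan's score: +30 and +29 ms with all late responses recorded, +6 and +3 ms with the deadline, -12 and -14 ms with omissions (-15 before rounding at tau 75).
- Percentile score with omissions dropped: as much as -12 and -14 ms.
- Percentile score with omissions ranked slowest: -3 to -4 ms throughout, within 210 to 217 ms.

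Omissions push the plan's score down because a missed response on a stop trial counts as a successful stop. At tau 50 the tracked delay rises from 226 to 238 ms, while the mean of the recorded Go RTs stays at 450 ms.

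**The case against.** The strongest reply is that the direction is not established. A reader might infer that THC-induced lapses would show up as impaired inhibition. That requires lapses to be recorded as very late responses with no effective deadline. The plan states neither a deadline nor an omission rule, and under a 1000-ms deadline the effect nearly vanishes, while under omissions it reverses. This stands.

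A reader might also infer that the Simple Reaction Time task is included because the investigators expect the drug or age to change the RT tail. The documents do not say so. They say that the task measures inattention and, of the doses, "These doses of THC are known to produce performance impairments as well as subjective intoxication". Nothing predicts a change in Go RT skew in the Stop Task, and every RT input above is assumed. This stands too.

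Mean Go RT and the lapse index give some context, but not protection. Mean Go RT cannot separate uniform slowing, which cancels, from added skew, which does not. The Simple Reaction Time task is not named among the tasks listed under Drug Administration Sessions (the list is not exhaustive), and no adjustment of Stop RT by its index is planned.

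Finally, a median or percentile score that drops omissions is no cure, since under omissions it shifts as far as the plan's score. That is a reason to specify the omission rule, not to keep the mean. None of this removes the algebraic point: the stated formula contains the mean-median gap, and nothing planned takes it out.

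**Conclusion.** The concern holds in a limited form. Given 50% tracking and the race model, the stated score is true Stop RT plus the mean-median gap in Go RT. A change in skew or in omissions by dose or age could therefore shift it with stopping ability unchanged. Neither the size nor the sign follows from the documents. Under the assumptions shown, 10% lapses move the score by anything from about -15 to +30 ms against a true 220 ms. A claim that the trial will report a false inhibition deficit, or false adolescent vulnerability, goes further than the text allows.

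The reach is also limited. Stop RT is the primary measure of this one task. The trial's primary outcome, the Feel item of the Drug Effects Questionnaire, and the sample size based on it are unaffected. The change is worth making because the stated rule is biased whenever Go RTs are skewed, and a better one costs little.

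**What to change.** In item 2 of Behavioral Measures, define Stop RT as the Go RT at the percentile equal to the observed response rate on stop trials, minus the mean delay. At exactly 50% responding this is the median of that Go RT distribution minus the mean delay. State the response deadline. State also that go omissions stay in the distribution and are ranked as the slowest responses, because without that rule the new score is not protected either. Keep mean Go RT as the secondary measure and report the mean-based Stop RT as a sensitivity analysis.

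The cost is a few sentences and a rescoring, with no added procedures for participants. It requires trial-level reaction times to be saved, which the documents do not confirm. Values will not be directly comparable with work scored from the mean unless both scores are reported. Make the change before unblinding, so that the choice of score cannot depend on the results.
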